8.1.6 Peripheral Neuropathy

Peripheral neuropathy associated with INH is usually avoided by the concurrent administration of vitamin B₆, and is expected to be rare given the once-weekly dosing and duration of the study drug regimen (12 weeks). In this study, all women will take vitamin B₆ as part of the complete study drug regimen. If peripheral neuropathy develops, every effort should be made to determine the etiology (i.e., to uncover other potential contributing factors such as alcohol use or concomitant drugs with this side effect). Women with Grade 1 peripheral neuropathy may be entered into the study, but should be monitored carefully for any progression of peripheral neuropathy.

Grade 1 or 2:

Continue the study drug regimen and assess the woman for progression of peripheral neuropathy.

Grade 3 or 4:

- Hold study drug regimen and assess weekly until toxicity resolves to Grade ≤ 2 ; then study drug regimen may be reintroduced at the site investigator's discretion.
- If peripheral neuropathy does not resolve to Grade ≤ 2 , then the study drug regimen can be discontinued or reintroduced at the site investigator's discretion.

8.1.7 Asymptomatic Elevations in AST/ALT

Every effort should be made to determine the etiology (i.e., whether the elevated AST/ALT is due to RPT/INH toxicity, alcohol, or other factors) in instances of suspected hepatotoxicity. Reintroduction of potential hepatotoxic non-study concomitant medications is at the discretion of the site investigator and the study participant. If a participant becomes symptomatic, follow guidance for symptomatic hepatitis.

Grade 1:

- Continue study drug regimen.
- Repeat test as soon as possible and within seven days.
- If repeat assessment is Grade ≤ 1 , continue study drug regimen.

Grade 2:

- Continue study drug regimen.
- Repeat test as soon as possible and within seven days.
 - Assess for alcohol use, non-study medication-related drug toxicity, lactic acidosis syndrome, pre-eclampsia, fatty liver of pregnancy, and viral hepatitis as the cause of the AST/ALT elevation. If the AST/ALT elevation is considered most likely to be due to concomitant illness or medication, standard management, including discontinuation of the likely causative agent, should be undertaken
- If repeat assessment is Grade ≤ 2 , continue study drug regimen.

Grade 3:

- Continue study drug regimen.
- Repeat test within three working days.
 - Assess for alcohol use, non-study medication-related drug toxicity, lactic acidosis syndrome, pre-eclampsia, fatty liver of pregnancy, and viral hepatitis as the cause of the AST/ALT elevation.
- If repeat assessment is Grade ≤ 2 , manage as per Grade 2.
- If repeat assessment is Grade 3 and is attributed to concomitant illness or medication (not related to study drug), study drug regimen may be continued at the discretion of the site investigator, and the Core Team notified. Treat the underlying illness or remove the likely causative agent.
- If the repeat assessment is Grade 3 and is assessed as related, hold study drug regimen.
 - Repeat testing weekly, and once the toxicity grade is Grade ≤ 2 , resume study drug regimen and notify the Core Team.
- When study drug regimen is resumed following a hold for Grade 3 AST/ALT, repeat testing should be performed one week after resumption. If the result of this testing is Grade 3 or 4, consult the Core Team.

Grade 4:

- Hold study drug regimen.
- Repeat test within three working days, in addition to total bilirubin and INR if available at the site.
 - Assess for alcohol use, non-study medication-related drug toxicity, lactic acidosis syndrome, pre-eclampsia, fatty liver of pregnancy, and viral hepatitis as the cause of the AST/ALT elevation.
- If repeat assessment is Grade < 4 , manage per the grade of the repeat assessment.
- If repeat assessment is Grade 4, continue to hold study drug regimen.
 - Repeat ALT/AST testing weekly, and consult the Core Team on study drug regimen and frequency of repeat assessments.
 - Once the repeat testing results in Grade ≤ 1 , resume study drug regimen.
- When study drug regimen is resumed following a hold for Grade 4 AST/ALT, repeat testing should be performed one week after resumption. If the result of this testing is Grade 3 or 4, consult the Core Team.

8.1.8 Hepatotoxicity (Symptomatic Hepatitis)

Signs and symptoms of hepatitis include but are not limited to fatigue, malaise, anorexia, nausea, acholic stools, bilirubinuria, jaundice, liver tenderness, and/or hepatomegaly (icteric sclera in isolation without systemic complaints would not be considered symptomatic).

- Hold study drug regimen.
- Immediately perform AST and ALT tests, in addition to total bilirubin and INR if available at the site; stored assays for hepatitis B/C should be processed. Follow general management guidelines based on the highest grade sign or symptom.
- Consult the Core Team on study drug regimen and frequency of repeat assessments (in general, at least weekly re-assessment is recommended).

8.1.9 HIV-1 Infection

Participants (i.e., women or infants) who become infected with HIV during the course of the study will be referred to local care for treatment. HIV-1-infected women who are changed from an EFV + 2 NRTI regimen by their HIV treatment provider and are prescribed a triple or quadruple NRTI regimen can continue to take study drugs as planned.

- Continue on study drug regimen, as long as they are not initiated on contraindicated medications (e.g., protease inhibitors).
- If not taking an EFV-based regimen, permanently discontinue the study drug regimen. Such women and their infants will remain on-study for follow-up visits to complete follow-up through 24 weeks postpartum. Infant feeding, prevention and treatment of HIV and other co-morbidities will also be according to local standard of care.

8.1.10 Postpartum Hemorrhage

There are multiple causes of postpartum hemorrhage. Rifampin, another rifamycin product, may increase the risk for maternal postpartum hemorrhage and bleeding in the exposed neonate. This has not been reported in mothers on rifapentine or rifampin-containing active TB regimens. As a precautionary measure, mothers will have their prothrombin time (PT) monitored at baseline, in late third trimester, and as clinically indicated during monthly follow-up. Infants will be monitored for PT at birth and as clinically indicated during monthly follow-up. If there is an increase in PT with associated prolonged bleeding in the mother or infant, treatment with vitamin K may be indicated as per local standard of care. For maternal postpartum hemorrhage or bleeding in infants:

Grade 1 or 2:

- Continue study drug regimen.
- Follow local standard of care and monitor PT.

Grade 3 or 4:

- Hold study drug.
- Assess for signs and symptoms of active bleeding and other pregnancy-related etiologies.
- If no signs of active bleeding or other etiologies of elevated PT are found, administer vitamin K per local standard of care and repeat PT within three working days.
- If repeat PT is \leq Grade 2, resume study drug regimen. Continue to monitor PT until it normalizes (i.e., returns to Grade 1 or lower).
- If repeat PT is \geq Grade 3, permanently discontinue study drug regimen. Continue to monitor PT until it normalizes (i.e., returns to Grade 1 or lower).
- If signs of active bleeding are found, permanently discontinue study drug regimen. Administer vitamin K per local standard of care. Continue to monitor bleeding and repeat PT until it is resolved to Grade 1 or lower.

Note: Postpartum hemorrhage is defined as blood loss greater than 500 mL in vaginal delivery and 1,000 mL in caesarean section within 24 hours of birth, at the discretion of the site investigator.

8.1.11 Pregnancy

For women who become pregnant again (during study follow-up) while still on the study drug regimen, permanently discontinue study drug regimen and refer to local standard of care. They will remain on-study and complete the study procedures and evaluations per the schedule, with follow-up through 24 weeks postpartum from the initial pregnancy. For women who are HIV-1-infected, the new pregnancy will be reported on the ARV Pregnancy Registry (<http://www.apregistry.com/>). At the end of this new pregnancy, site staff will contact the woman so the pregnancy outcome can be recorded on a CRF.

8.1.12 General Management of Adverse Events (Not Otherwise Specified) - Mothers

Grades 1 and 2:

A woman who develops a Grade 1 or 2 AE (regardless of relatedness to study drug regimen) may continue the study drug regimen at the discretion of the site investigator.

Grades 3 and 4:

Study drug regimen should be temporarily held until the AE returns to baseline (enrollment visit levels) if baseline was $>$ Grade 2, until \leq Grade 2, or within normal limits if baseline was \leq Grade 2. If the Grade 3 or 4 AE does not resolve within four weeks, then the study drug regimen may be permanently discontinued and the Core Team notified.

8.2 Criteria for Premature Permanent Discontinuation of Study Drug

In the event of treatment discontinuation, women and their infants will remain on-study but off study treatment to complete follow up for 24 weeks postpartum.

- Participant has been confirmed as having developed active pulmonary or extrapulmonary TB, per Gene Xpert, shielded chest x-ray, or AFB sputum smear microscopy, or other available TB diagnostics
- Drug toxicity requires permanent study drug discontinuation as defined in Section 8.1 above
- Repeat pregnancy during study follow-up
- For HIV-1-infected women, not taking an EFV-based HIV regimen
- If the woman chooses to discontinue the study drug regimen, the Core Team should be notified within 48 hours. The site should complete the evaluations specified in Section 6.10 within seven days after stopping the study drug regimen.

8.3 Criteria for Premature Discontinuation of Study Participation

A participant must be withdrawn from study participation if:

- The participant withdraws consent and/or does not wish to continue in the study.
- The site investigator determines further participation would be detrimental to the participant's health or well-being.
- The participant fails to comply with study requirements, so as to cause harm to self or seriously interfere with the validity of the study results.
- The study is cancelled at the discretion of IMPAACT, the Food and Drug Administration (FDA), NIAID, the Office for Human Research Protections (OHRP), the local and/or national IRB or EC, or a country-specific governmental agency.

Note: Lost to follow-up is defined as a participant having missed four or more consecutive study visits without contact with study staff.

See Section 6.10 for procedures to be conducted in the event of premature discontinuation of study participation.

9 STATISTICAL CONSIDERATIONS

9.1 General Design Issues

This study is a Phase I/II, open-label, multi-center, intensive PK study to evaluate the pharmacokinetics, safety, and tolerability of RPT and INH dosed once weekly for 12 doses in HIV-1-infected and HIV-1-uninfected pregnant women with latent TB infection at high risk for development of TB. Infants will also be enrolled, and breast milk samples from postpartum women who are still taking RPT/INH will be collected.

Two study cohorts are planned:

- Cohort 1: Pregnant women ≥ 14 weeks gestation through < 28 weeks gestation (second trimester)
- Cohort 2: Pregnant women ≥ 28 weeks gestation through ≤ 34 weeks gestation (third trimester)

An interim analysis to assess the PK of RPT will be conducted, and a dose adjustment may be indicated for each cohort. Dose adjustments indicated for Cohort 2 will be implemented for Cohort 1 women as they enter their third trimester of pregnancy. See Section 3.4 for accrual into the cohorts, and Section 10 (Clinical Pharmacology Plan) for further details regarding the interim analysis and dose adjustment.

In this section, only analyses related to Objectives 2.1.2, 2.1.3, 2.2.4, 2.2.6, and 2.2.7 are described. All other analyses are described in Section 10, as they are pharmacology objectives.

Primary analyses in this study estimate pharmacokinetic parameters cross-sectionally and longitudinally. The fundamental concern is to assess maintenance of drug levels between second and third trimesters of pregnancy, along with assessment of postpartum drug levels in women and infants. Dose-exposure relationships will be modeled, concentrations in infant blood samples and breast milk will be quantified, and safety-related event rates will be estimated.

9.2 Outcome Measures

The primary outcome measures for pregnant women during the second trimester, third trimester, and postpartum period who are receiving a dose of RPT 900mg once weekly together with once-weekly INH (900mg) are detailed below. All outcome measures will be collected and recorded on the CRFs according to standard IMPAACT procedures and transmitted to the Data Management Center for inclusion in standard database tables. Standard quality assurance procedures will be followed throughout the data lifetime.

9.2.1 Primary Outcome Measures

9.2.1.1 Estimates of CL/F, absorption, and volume of distribution of RPT and its desacetyl-rifapentine metabolite (desRPT).

9.2.1.2 Safety (maternal)

- Incidence of related serious adverse events (SAEs) in pregnant and postpartum women taking once-weekly RPT + INH
- Grade 2 adverse events (AEs) judged to be related to study drug regimen
- All Grade 3 and 4 AEs
- All serious AEs
- All AEs leading to permanent discontinuation of study drug regimen (i.e., RPT, INH, and pyridoxine)

9.2.1.3 Safety (infant)

Incidence of related serious adverse events (AEs) in infants born to women taking once-weekly RPT + INH.

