2 OBJECTIVES

2.1 Primary Objectives

- 2.1.1 To estimate the population pharmacokinetics (PK) (CL/F, absorption, volume of distribution) of RPT and its desacetyl-rifapentine metabolite (desRPT) among pregnant women during the second trimester and third trimester who are receiving once-weekly RPT (900mg or the new study dose, if a dose adjustment is indicated by the interim analysis) and once-weekly INH (900mg).
- 2.1.2 To estimate the incidence of serious adverse events (SAEs) related to RPT + INH dosed once weekly for 12 weeks in pregnant women.
- 2.1.3 To describe the infant safety outcomes among infants born to women receiving once-weekly RPT + INH.

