Diagnoses: All diagnoses identified from the Screening Visit through immediately prior to the first administration of study drug regimen, except Grade 1 and Grade 2 diagnoses listed on the IMPAACT Do Not Record list (available at www.fstrf.org), will be recorded as pre-existing conditions on the relevant CRF. During follow-up through the Study Exit Visit, all diagnoses since the last study visit except Grade 1 and Grade 2 diagnoses listed on the IMPAACT Do Not Record list will be recorded on the relevant CRF. In addition, throughout follow-up, Grade 2 or higher diagnoses related to pregnancy complications, hepatotoxicity, hemorrhage, or peripheral neuropathy, all Grade 3 or higher diagnoses, diagnoses that result in discontinuation of study drug regimen, and diagnoses that meet criteria for EAE reporting (including congenital anomalies) will be further evaluated, with additional data recorded on the relevant event evaluation CRF. All diagnoses recorded on CRFs should be recorded consistent with the specifications of the relevant diagnosis appendix (available at www.fstrf.org).

With appropriate permission of the participant/mother, whenever possible, records from all non-study medical providers related to untoward medical occurrences will be obtained and required data elements will be recorded on study CRFs.

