7.3.3 Grading Severity of Events

Severity and laboratory tests will be graded per the DAIDS Table for Grading Adult and Pediatric Adverse Events, Version 2.0 (dated November 2014 available on the RSC website (<http://rsc.tech-res.com/safetyandpharmacovigilance/>), except for complications during pregnancy. Complications during pregnancy will be graded per the Complications of Pregnancy Section of the Female Genital Grading Table for Use in Microbicide Studies (Version 1.0, dated November 2007) found on the DAIDS RSC website (<http://rsc.tech-res.com/safetyandpharmacovigilance/gradingtables.aspx>).

For any serious or expedited AEs (SAEs/EAEs) that are continuing at a participant's study exit visit, the IoR/designee must establish a clinically appropriate follow-up plan for the AE, including referrals to local standard of care. The same approach must be taken for any AEs that are found to have increased in severity at the time of the study exit visit or continue requiring re-assessments beyond the study exit visit.

Serious adverse events (SAEs) will be defined by the Manual for Expedited Reporting of Adverse Events to DAIDS (Version 2.0, January 2010), as AEs occurring at any dose that:

- Results in death
- Is life-threatening
- Requires inpatient hospitalization or prolongation of existing hospitalization
- Results in persistent or significant disability/incapacity
- Is a congenital anomaly/birth defect
- Is an important medical event that may not result in death, be immediately life-threatening, or require hospitalization but may jeopardize the participant or require intervention to prevent one of the outcomes listed in the definition above

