9.7.2 Safety Outcomes

The primary safety analysis will include all women who have been exposed to RPT/INH at any dose in the study. Women whose doses have been adjusted for inadequate PK will be included in the primary safety analysis. Women who have been removed from treatment due to toxicities while on the optimal dose will be included and treated as safety failures in the primary safety analysis. Additional analyses will look at the combined data from women whose doses failed and those who have been treated solely at the optimal doses determined for their cohorts. Each woman's safety data will be summarized as: the worst grade of adverse event experienced during study treatment and the worst grade of adverse event judged to be at least possibly related to study treatment during this time period.

Frequency distributions of these safety outcomes will be presented in the aggregate and broken down by cohort. Listings of all \geq Grade 3 or ICH defined serious events will be provided. The proportions of participants experiencing \geq Grade 3 or ICH defined serious adverse events will be presented in aggregate and broken down by cohort, with these proportions bounded by exact 95% confidence intervals. Similar analyses will present the proportions of participants exhibiting \geq Grade 3 or ICH defined serious events which have been judged to be at least possibly related to study medication, again bounded by exact 95% confidence intervals.

For objectives 2.1.2, 2.1.3, and 2.2.6, Poisson regression will be used to estimate the incidence of serious adverse events related to treatment, adjusting for important cofactors. Analyses of tolerability and safety for infants will employ standard descriptive techniques; events of intolerability or compromise to infant safety are expected to be rare.

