10.5 Primary and Secondary Data Analysis Plan

Primary: Pharmacokinetic data (concentration-time data) and safety data of rifapentine and desacetyl-rifapentine in pregnant women; safety outcomes in infants

Secondary: Pharmacokinetic data of rifapentine and desacetyl-rifapentine in postpartum women and infants; pharmacokinetic data of isoniazid in pregnant and postpartum women

Population-based estimates of RPT CL/F, absorption, and volume of distribution will be derived for pregnant women in second and third trimesters of pregnancy and in the postpartum period. Study data will provide a mix of longitudinal and cross-sectional observations, which will be combined using standard algorithms in wide use in pharmacology research. The pharmacokinetics of the desacetyl-rifapentine (des-RPT) metabolite of RPT and INH will be estimated based on the sample in like fashion. Rates of adverse events and other safety-related parameters will be computed and reported for study monitoring and regulatory use. Secondary objectives are: characterization of PK data of RPT and des-RPT in the postpartum period, description of adverse and safety outcomes in pregnant women, assessment of impact of covariates on primary PK parameters, comparison of RPT and des-RPT exposures between study participants and non-pregnant historical controls, estimation of effective RPT dose for pregnant women, estimation of RPT concentrations in newborns, description of pregnancy and infant safety outcomes, description of RPT + INH tolerability in pregnancy, and characterization of PK data of INH in pregnant and postpartum women.

The primary tool for estimation of parameters of interest is the single compartment model for RPT absorption and disposition kinetics:

$$\frac{dA(1)}{dt} = -ka \times A(1); \text{ Absorption compartment}$$
$$\frac{dA(2)}{dt} = ka \times A(1) - \frac{CL}{V} \times A(2); \text{ Central Plasma compartment}$$

The parameters CL and V will be elaborated upon to incorporate allometric scaling and effects of gestational age.

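### The only infant safety outcome counts related SAEs in infants born, which is narrower than the primary objective and the maternal measure; all-cause infant events and birth outcomes have no measure of their own

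*Protocol*

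**What the plan says.** Primary objective 2.1.3 of the protocol is "To describe the infant safety outcomes among infants born to women receiving once-weekly RPT + INH". The one outcome measure that serves it, in 9.2.1.3, is "Incidence of related serious adverse events (AEs) in infants born to women taking once-weekly RPT + INH".

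The maternal measure in 9.2.1.2 also starts with related SAEs, but adds "All serious AEs" and "All Grade 3 and 4 AEs", neither limited by attribution.

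Section 10.5 includes "description of pregnancy and infant safety outcomes" among the secondary objectives. Section 2.2 lists no such objective, and 9.2.2 has no measure for it.

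Section 9.7.2 names objective 2.1.3 among those to be analysed by Poisson regression of treatment-related SAEs. It then says "Analyses of tolerability and safety for infants will employ standard descriptive techniques", without naming variables.

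The SAP supplied is a pharmacokinetic plan. It mentions safety data in its objectives but specifies no safety analysis.

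**The concern.** The infant measure has two filters that the objective does not call for: the event must be serious, and it must be judged related. The second matters more. Section 7.3.3 makes death and congenital anomaly SAEs by definition. Under 8.1, however, an event can be classed as probably not related while a link to the drug is still possible, and 9.6.2 counts only definite, probable and possible relationships as drug-related. An anomaly or neonatal death classed as probably not related therefore leaves the primary infant outcome by rule.

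The trial has one open-label regimen and no concurrent control, and the protocol's introduction says that the regimen's safety in pregnancy is unknown. In that setting, individual attribution is a weak basis for the only infant measure. The introduction also points out that earlier rifapentine studies did not have pregnancy outcomes as a primary outcome, and its Table 2 tabulates pregnancy outcomes without regard to attribution. Section 9.2 provides nothing comparable. At stake is whether the report can say what happened to the infants and pregnancies, or only how many events were attributed to the drug.

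**Working it through.** **1. Coverage, outcome by outcome**

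| Event | Recorded? | Measure in 9.2 that reports it as such |
|---|---|---|
| Related infant SAE | Yes (7.2, 8.1) | 9.2.1.3 |
| Infant SAE or death judged not related | Yes (7.2, 8.1) | None |
| Grade 3-4 infant event, not a related SAE | Yes (7.2, 8.1) | None |
| Congenital anomaly judged not related | Yes (6.7.2; an SAE under 7.3.3) | None |
| Preterm birth, low birth weight | Gestational age and birth weight recorded (6.7.2) | None |
| Fetal loss, stillbirth | As a pregnancy complication or adverse event (7.2, 7.3.3) | None; it may count as a maternal SAE or Grade 3-4 event |

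On the last row, 7.3.3 says "Complications during pregnancy will be graded per the Complications of Pregnancy Section of the Female Genital Grading Table for Use in Microbicide Studies", and 7.2 sends "Grade 2 or higher diagnoses related to pregnancy complications, hepatotoxicity, hemorrhage, or peripheral neuropathy" for further evaluation on an event form. A fetal loss therefore has a route into the maternal counts. Its grade depends on an external table, so capture is likely but not certain, and it would not be shown as a fetal loss. One maternal summary in 9.7.2, the worst grade per woman, covers only the treatment period. A woman who starts at 14 weeks and takes 12 weekly doses on schedule has her last dose at week 14 + 11 = 25, so a later stillbirth falls outside that summary.

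**2. The plan's own figure**

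Section 9.5.2 gives 90% power to see at least one event at a true rate of 5 per 100 with 50 women or infants.

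- Poisson: 1 − exp(−50 × 0.05) = 1 − exp(−2.5) = 91.8%.
- Exact binomial: 1 − 0.95^50 = 92.3%.
- Table 4, Poisson minimum n for 90% at 5%: ln(10)/0.05 = 46.05, so 47, as printed. The other 11 cells also reproduce on the Poisson basis.

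The stated figure holds for an event with a 5% rate.

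**3. Effect of the attribution filter**

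Let q be the all-cause infant SAE rate and f the share judged related. Neither is in the documents; both are assumptions. The chance of counting at least one event among 50 infants is 1 − (1 − q·f)^50.

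| q | f = 1 | f = 0.5 | f = 0.2 |
|---|---|---|---|
| 5% | 92.3% | 71.8% | 39.5% |
| 10% | 99.5% | 92.3% | 63.6% |

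For example, at q = 5% and f = 0.5: 1 − 0.975^50 = 71.8%.

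**4. What a count of zero related events would say**

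The exact (Clopper-Pearson) upper 95% bound for zero events in n is 1 − 0.025^(1/n).

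- n = 50, the evaluable target: 7.1%.
- n = 82, the enrolment ceiling: 4.4%.

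The larger n is relevant because 9.5.2 and 9.7.2 put every woman exposed to study drug in the safety analysis. In either case the bound applies to related SAEs only and is the same whatever unattributed events occurred.

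**5. What the added measures would deliver**

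At 50 pregnancies, exact 95% intervals for illustrative counts are: 0/50, 0 to 7.1%; 2/50, 0.5 to 13.7%; 5/50, 3.3 to 21.8%. These are wide, but adequate for a descriptive statement.

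**The case against.** A reader might infer that fetal losses and adverse birth outcomes escape every outcome measure. The documents do not support that. The maternal counts of all SAEs and all Grade 3-4 events ignore attribution, and pregnancy complications are graded and recorded. Section 9.7.2 also promises listings of Grade 3 or higher or serious events, and proportions of participants with them, with exact 95% intervals and without regard to attribution; the related events are a second analysis. Elsewhere (for example 4.3 and 6.7.1) the protocol uses the word participants for women and infants alike. But the surrounding paragraphs of 9.7.2 are about women, so whether infants are covered is left open. This objection narrows the point to the absence of a named measure.

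A second tempting reading is that leaving out fetal loss fails objective 2.1.3. It does not: the objective itself is limited to infants born. The mismatch over fetal loss is with the phrase in 10.5, not with Section 2. Infants are, however, enrolled in utero with their own study number (4.4 and 6), so a per-pregnancy denominator already exists.

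Third, attribution does not rest on the site clinician alone. Under 9.6.2 the protocol team determines the relationship of Grade 3 or higher events, disagreements are reconciled, unresolved cases go to the monitoring committee, and a possible relationship counts as related. That is a fairly low threshold. These safeguards stand, though the team also works without a concurrent control. Nothing in the documents shows that a drug effect would tend to be classed as unrelated, so that should not be claimed.

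Fourth, the Poisson and descriptive sentences in 9.7.2 need not conflict. The first can cover related-SAE incidence and the second everything else for infants. Clarification is enough; the Poisson text need not be deleted.

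Finally, making every birth outcome primary in a single-arm study would go too far, because background rates have no comparator here. Entry criteria (a viable singleton pregnancy from 14 weeks, no known major fetal abnormality) also remove early losses and known anomalies, so general-population rates would not be a fair yardstick.

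**Conclusion.** The concern holds in a limited form. The infant outcome in 9.2.1.3 is narrower than objective 2.1.3 and than the parallel maternal measure, and no reason is given. No measure in 9.2 reports, as such, all-cause infant SAEs or deaths, all-cause anomalies, preterm birth, low birth weight or fetal loss. Fetal loss may be captured indirectly as a maternal event, and all-cause infant events may be covered by the tables in 9.7.2 if these are read to include infants.

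No stated figure is wrong, and the sample size is not in question. The size of the effect depends on an unknown share of events judged related. At an all-cause rate of 5%, with shares of one half and one fifth, the chance that 50 infants yield at least one counted event is 71.8% and 39.5%, against 92.3% with no filter. These are illustrations under assumed values. The SAP supplied covers pharmacokinetics only, so detailed safety tables cannot be judged from it. The change should be made because it is cheap and lessens dependence on attribution.

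**What to change.** - **9.2.1.3:** add all infant SAEs, including deaths and congenital anomalies, and all infant events of Grade 3 or higher, irrespective of attribution. Keep related SAEs as a subset.
- **9.2.2:** add descriptive secondary measures: fetal loss or stillbirth per enrolled pregnancy, and preterm birth and low birth weight per live birth, each with an exact 95% interval. Define each term, since the protocol gives no definition of preterm birth or low birth weight.
- **9.7.2:** state that the all-cause listings and exact intervals apply to infants as well as women. State that Poisson regression applies only to related-SAE incidence and that other infant outcomes are descriptive.

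The cost is wording and tables. Birth weight, gestational age and anomalies are already collected under 6.7.2. A field for the outcome of the index pregnancy may be needed, because 8.1.11 explicitly requires that entry only for a repeat pregnancy. The drawback is that background events will be shown without a control arm, so the text should present them as descriptive.
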